#### 11.10 Adverse Event Documentation

Adverse events will use the descriptions and grading scales found in the revised NCI Common Terminology Criteria for Adverse Events (CTCAE). This study will utilize the CTCAE Version 4.0 for adverse event reporting.

Documentation of each adverse event must be supported by an entry in the patient's file. Each event should be described in detail along with start and stop dates, severity, relationship to investigational product as judged by the Investigator, action taken and outcome.

#### 11.11 Causality of AEs

The causal relationship to study drug is determined by a physician and should be used to assess all adverse events (AE). The casual relationship can be one of the following:

- Related: There is a reasonable causal relationship between study drug administration and the AE.
- Not related: There is not a reasonable causal relationship between study drug administration and the AE.

The term "reasonable causal relationship" means there is evidence to suggest a causal relationship.

#### 11.12 Serious Adverse Event

Reporting of SAEs is detailed in Section 17.2.

Clarification should be made between the terms *serious* and *severe* because they are not the same. The term *severe* is often used to describe the intensity (severity) of a specific event (as in mild, moderate, or severe myocardial infarction); the event itself, however, may be of relatively minor medical significance (such as a severe headache). This is not the same as *serious*, which is based on the patient/event outcome or an action criterion described above, and is usually associated with events that pose a threat to a patient's life or functioning. A severe AE does not necessarily need to be considered serious. For example, persistent nausea of several hours duration may be considered severe nausea but may not be considered an SAE. On the other hand, a stroke resulting in only a minor degree of disability may be considered mild but would be defined as an SAE based on the above noted criteria. Seriousness (not severity) serves as a guide for defining regulatory reporting obligations.

Following the patient's written consent to participate in the study, all SAEs, whether related or not related to study drug, must be collected, including those thought to be associated with protocol-specified procedures. All SAEs must be collected that occur during the screening period and within 100 days of discontinuation of dosing. If applicable, SAEs must be collected that relate to any later protocol-specified procedure (e.g., a follow-up skin biopsy). All SAEs should be followed to resolution or stabilization.

A **Serious** Adverse Event or Reaction is any AE occurring at any dose that:

- Results in death

- Is life-threatening (defined as an event in which the patient was at risk of death at the time of the event; it does not refer to an event that hypothetically might have caused death if it were more severe)
- Requires inpatient hospitalization or prolongation of existing hospitalization EXCEPT as noted below
- Results in persistent or significant disability/incapacity (defined as substantial disruption of a person's ability to conduct normal life's functions).
- Results in a congenital anomaly / birth defect
- Results in anaphylaxis related to study drug
- Results in an important medical event that may not be immediately life threatening or result in death or hospitalization, but may jeopardize the patient and may require medical or surgical intervention to prevent one of the outcomes listed above (example: intensive treatment in an emergency room or at home for bronchospasm, convulsions that do not result in hospitalization). Medical and scientific judgment should be exercised in deciding whether some events should be considered as serious because their quick reporting to the sponsor may be of interest for the overall conduct of the study. Examples of such events include, but are not limited to, intensive treatment in an emergency room or at home for allergic bronchospasm, blood dyscrasias or convulsions that do not result in hospitalization, or drug-induced liver injury.
- Results in suspected transmission of an infectious agent (pathologic or nonpathologic) via the study drug

**Hospitalization:** Any adverse event leading to hospitalization or prolongation of hospitalization will be considered an SAE, UNLESS at least one of the following exceptions is/are met:

- A visit to the emergency room or other hospital department <24 hours that does not result in admission (unless considered an important medical or life-threatening event).
- Elective surgery, planned prior to signing consent
- Admissions for a planned medical/surgical procedure as part of the study protocol
- Routine health assessment requiring admission for baseline/trending of health status (e.g. colonoscopy).
- Medical/surgical admission other than to remedy ill health and planned prior to entry into the study. Appropriate documentation is required in these cases
- Admission encountered for another life circumstance that carries no bearing on health status and requires no medical/surgical intervention (e.g. lack of housing, economic inadequacy, caregiver respite, family circumstances, administrative reason).

It should be noted that invasive treatment during any hospitalization may fulfil the criteria of 'medically important' and as such may be reportable as a serious adverse event dependant

on clinical judgement. In addition where local regulatory authorities specifically require a more stringent definition, the local regulation takes precedent.

**Pregnancies** occurring in study patients/sexual partner(s) will be treated procedurally as SAEs and patient is required to immediately discontinue the trial medication. **Overdoses** and **Potential Drug Induced Liver Injury (DILI)** should also be reported as an SAE.

#### 11.13Pregnancy

If, following initiation of nivolumab or ipilimumab, it is subsequently discovered that a study subject is pregnant or may have been pregnant at the time of investigational product exposure, including during at least 6 half lives after product administration, nivolumab and ipilimumab will both be permanently discontinued.

Protocol-required procedures for study discontinuation and follow-up must be performed on the subject unless contraindicated by pregnancy (e.g., x-ray studies). Other appropriate pregnancy follow-up procedures should be considered if indicated.

The investigator must immediately notify Worldwide Safety @BMS of this event via the Pregnancy Surveillance Form in accordance with SAE reporting procedures described in Section 17.2.1.

Follow-up information regarding the course of the pregnancy, including perinatal and neonatal outcome and, where applicable, offspring information must be reported on the Pregnancy Surveillance Form [provided upon request from BMS].

Any pregnancy that occurs in a female partner of a male study participant should be reported to BMS. Information on this pregnancy will be collected on the Pregnancy Surveillance Form.

#### 11.14Overdose

An overdose is defined as the accidental or intentional administration of any dose of a product that is considered both excessive and medically important. All occurrences of overdose must be reported as an SAE (see Section 17.2.1 for reporting details.).

#### 11.15Potential Drug Induced Liver Injury (DILI)

Wherever possible, timely confirmation of initial liver-related laboratory abnormalities should occur prior to the reporting of a potential DILI event. All occurrences of potential DILIs, meeting the defined criteria, must be reported as SAEs (see Section 17.2.1 for reporting details).

Potential drug induced liver injury is defined as:

- 1) ALT or AST elevation > 3 times upper limit of normal (ULN)  
AND
- 2) Total bilirubin > 2 times ULN, without initial findings of cholestasis (elevated serum alkaline phosphatase)  
AND

- 3) No other immediately apparent possible causes of AST/ALT elevation and hyperbilirubinemia, including, but not limited to, viral hepatitis, pre-existing chronic or acute liver disease, or the administration of other drug(s) known to be hepatotoxic.

#### 11.16 Events NOT to be reported as SAEs

For this study, the following are **not** classified as serious adverse events

- Progression or deterioration of the malignancy under study (including new metastatic lesions) or death due to disease progression.
- Hospitalization for the performance of protocol-required procedures or administration of study treatment, including any hospitalization required for pre-treatment tumor resection. However, hospitalization or a prolonged hospitalization for a complication of therapy administration will be reported as an SAE.
- Hospitalization or procedures planned prior to start of study therapy, including any hospitalization required for pre-treatment tumor resection. A pre-planned procedure must be documented in the source documents. However, hospitalization or prolonged hospitalization for a complication remains to be reported as an SAE.
- An elective hospitalization for a pre-existing condition unrelated to the studied indication.
- Hospital admission that is not associated with an adverse event (e.g. social hospitalization for purpose of respite care).
- Routine treatment or monitoring of the studied indication not associated with any deterioration in condition.
- The administration of blood or platelet transfusion as routine treatment of studied indication. However, hospitalization or prolonged hospitalization for a complication of such transfusions remains to be reported as an SAE.
- Emergency outpatient treatment or observation that does not result in admission, unless fulfilling other seriousness criteria above.

#### **12.1 CRITERIA FOR THERAPEUTIC RESPONSE/OUTCOME ASSESSMENT**

Best overall response rate (confirmed partial + complete response) will be assessed as part of this study. Tumor response will be assessed using RECIST 1.1. All responses must be confirmed on subsequent scan to be considered a true response.

The same CT method with the same technique (i.e. with or without contrast) should be used to characterize each identified and reported lesion at baseline and every 6 weeks (+/- 1 week) thereafter while on study until week 48. After week 48, tumor assessments will be conducted every 12 weeks (+/- 1 week). Tumor assessments should be scheduled irrespective of dose delays/treatment interruptions. Designated radiologists/physician will be responsible for interpretation of the study imaging according to RECIST 1.1.

A CT scan of the chest or CT chest (+/- abdomen/pelvis depending on sites of known disease) with or without contrast will be performed to demonstrate all known areas of measurable disease. The baseline study will occur no more than 4 weeks prior to first study drug administration. An alternative imaging test, including MRI, can also be used in patients with contraindications to radiographic contrast media used in CT scans. PET scans or bone scans are not adequate for assessment of RECIST 1.1 response in target lesions. All patients must have at least one measurable disease lesion by CT or MRI.

Target Lesions:

All measurable lesions, up to a maximum of 5 lesions total, representative of all involved organs should be identified as target lesions and recorded and measured at baseline. Target lesions should be selected on the basis of their size, should be representative of all involved organs, and should lend themselves to reproducible repeat measurements. All other lesions (or sites of disease) should be identified as non-target lesions and should also be recorded at baseline as well. All baseline evaluations should be performed as close as possible to the start of treatment and never more than 28 days prior to beginning treatment.

All measurements should be recorded in millimeters. A sum of the diameters (longest for non-nodal lesions, short axis for nodal lesions) for all target lesions will be calculated and reported as baseline sum diameters. If lymph nodes are to be included in the sum, then only the short axis is added into the sum. The baseline sum diameters will be used as reference to further characterize any objective tumor regression in the measurable dimension of the disease.

Non-Target Lesions:

All other lesions (or sites of disease) including pathological lymph nodes should be identified as non-target lesions and should be also recorded at baseline. Measurements are not required and these lesions should be followed as “present,” “absent,” or in rare cases “unequivocal progression.” In addition, it is possible to record multiple non-target lesions involving the same organ as a single item (e.g. “multiple enlarged pelvic lymph nodes”).

Tumor Response Evaluation:

Definitions of response in target and non-target lesions are described in Table 12.1 and 12.2 below. Table 12.3 provides overall responses for all possible combinations of tumor responses in target and non-target lesions.

Table 12.1: Evaluation of target lesions	
Complete Response (CR):	Disappearance of all target lesions
Partial response (PR)	At least a 30% decrease in the sum of the diameters of the target lesions
Progressive disease (PD):	At least a 20% increase in the sum of the diameter of the target lesions or the appearance of one or more new lesions
Stable disease (SD):	Neither sufficient shrinkage to qualify for PR nor sufficient increase to qualify for PD

Table 12.2: Evaluation of non-target lesions	
Complete Response (CR):	Disappearance of all non-target lesions
Incomplete response/Stable disease (SD):	Persistence of one or more non-target lesions
Progressive disease (PD):	Appearance of one or more new lesion and/or unequivocal progression of existing non-target lesion

Table 12.3: Combinations of responses			
Target lesions	Non-target lesions	New lesions	Overall response
CR	CR	No	CR
CR	Incomplete/SD	No	PR
PR	Non-PD	No	PR
SD	Non-PD	No	SD
PD	Any	Yes or No	PD
Any	PD	Yes or No	PD
Any	Any	Yes	PD

Evaluation of Non-Target Lesions:

Although some non-target lesions may actually be measurable, they need not be measured and instead should be assessed only qualitatively at the time points specified in the protocol.

**Complete Response (CR):** Disappearance of all non-target lesions. All lymph nodes must be non-pathological in size (< 10 mm short axis).

**Non-CR/Non-PD:** Persistence of one or more non-target lesion(s) above the normal limits.

**Progressive Disease (PD):** Unequivocal progression of existing non-target lesions (Note: the appearance of one or more new lesions is also considered progression). To achieve ‘unequivocal progression’ on the basis of the non-target disease, there must be an overall level of substantial worsening in non-target disease such that, even in presence of SD or PR in target disease, the overall tumor burden has increased sufficiently to merit discontinuation of therapy. A modest ‘increase’ in the size of one or more non-target lesions is usually not sufficient to qualify for unequivocal progression status.

Confirmation of Scans

**Verification of Response:** Initial observations of response will be confirmed by repeat scans which should be performed no earlier than 4 weeks after the original observation to ensure that responses identified are not the result of measurement error. After an initial PR or CR is noted, the subsequent protocol-specified tumor assessment may serve as the confirmation.

**Verification of Progression:** Progression of disease should be verified in cases where progression is equivocal. If repeat scans confirm PD, then progression should be declared using the date

of the initial scan. If repeat scans do not confirm PD, then the subject is considered not to have progressive disease per RECIST 1.1.

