#### **Lesions which become too small to measure:**

- If the radiologist is able to provide an actual measurement, that should be recorded, even if below 5 mm.
- However, when a lesion becomes difficult to assign an exact measurement, then:
  - If it is the opinion of the radiologist that the lesion has likely disappeared, the measurement should be recorded as 0.
  - If the lesion (including lymph nodes) is believed to be present and is faintly seen, but too small to characterize, a default value of 5mm should be assigned.

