#### **Non-measurable lesions:**

- The following are considered non-measurable lesions:
  - Small lesions with longest diameter <10mm or pathologic lymph nodes with  $\geq 10$  to < 15 mm short axis
  - Leptomeningeal disease
  - Ascites
  - Pleural or pericardial effusion
  - Lymphangitic involvement of skin or lung
  - Abdominal masses/organomegaly identified by physical exam that is not measurable by reproducible imaging techniques

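### Table 12.1 scores target-lesion progression on a 20% relative increase with no minimum absolute increase, so a sole 10 mm lesion read as 12 mm is progression

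*Combined protocol and SAP*

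**What the plan says.** Section 12.1 states "Tumor response will be assessed using RECIST 1.1" and then writes out its own tables. The PD row of Table 12.1 reads "At least a 20% increase in the sum of the diameter of the target lesions", or one or more new lesions. It gives no millimetre minimum and does not say which earlier sum the increase is measured from. The only stated reference concerns shrinkage: "The baseline sum diameters will be used as reference to further characterize any objective tumor regression". The worked examples of growth in Sections 4.3, 9.1 and 13.0 count from baseline.

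On lesion size, "All patients must have at least one measurable disease lesion by CT or MRI", and the non-measurable list includes "Small lesions with longest diameter <10mm", so a single 10 mm non-nodal target is enough. "All measurements should be recorded in millimeters". For a follow-up lesion that is faintly seen but too small to characterise, "a default value of 5mm should be assigned". A millimetre threshold does exist for new lesions (10 mm, or 15 mm short axis for nodes), but none exists for growth of existing ones.

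On repeat imaging, every response must be confirmed, and the stated reason is measurement error. For progression the rule is narrower: "Progression of disease should be verified in cases where progression is equivocal". A PD that a repeat scan does not confirm is withdrawn, and the PFS definition applies this to patients who stay on therapy after the first PD scan.

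**The concern.** A purely relative threshold becomes very small in absolute terms when the sum is small. If 20% of the sum is about the size of ordinary reading variation, a stable tumour can be scored as progressing by chance, and more chances accrue with every scan. The plan guards responses against measurement error by confirming all of them, but gives progression less protection.

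Two endpoints are exposed. PFS takes an event at the first PD scan unless a repeat scan withdraws it. Best overall response in Section 12.1 counts only designations up to documented progression, so a false PD before a true response could exclude that response. At the 20-30% response rate quoted in the background for this combination, 30 patients give 30 x 0.20 = 6 to 30 x 0.30 = 9 responders, so even one lost responder would be noticeable.

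**Working it through.** The plan states no error rate for this rule, so there is no figure of its own to reproduce.

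**1. Millimetres needed for PD.** Increase needed = 0.20 x reference sum.

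| Reference sum (mm) | 20% of sum (mm) | With an added 5 mm minimum (mm) |
|---|---|---|
| 10 | 2 | 5 |
| 15 | 3 | 5 |
| 20 | 4 | 5 |
| 25 | 5 | 5 |
| 30 | 6 | 6 |
| 50 | 10 | 10 |

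For a sole 10 mm lesion, 11/10 = 1.10 is not PD and 12/10 = 1.20 is PD. A 5 mm minimum matters only below 5/0.20 = 25 mm.

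**2. One comparison, unchanged lesion.** Assume independent normal reading error with SD s. The difference of two readings then has SD s x sqrt(2), and P(false PD) = 1 - Phi(0.20 x S / (s x sqrt(2))), where S is the reference sum. For S = 10 and s = 1 this is 1 - Phi(2/1.414) = 7.9%. At s = 0.5, 1.5 and 2 it is 0.2%, 17.3% and 24.0%. With the 5 mm minimum the numerator becomes 5, which gives 0.02%, 0.9% and 3.9% at s = 1, 1.5 and 2.

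**3. Over the scan schedule.** Six-weekly scans to week 48 give 48/6 = 8 reads. The simulation used 200,000 stable single lesions per setting, readings rounded to whole millimetres, the baseline reading held at 10 mm or more, and PD scored against baseline. The reading SD of 0.75 to 1.0 mm is an assumption; the documents give none.

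| True size (mm) | At least one false PD in 8 scans |
|---|---|
| 10 | about 13-30% |
| 15 | 6-19% |
| 20 | 0.5-4% |
| 30 or more | about 0 |

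With the 5 mm minimum the chance is at most 0.6% at every size. At an SD of 1.5 mm and a 10 mm lesion, it is 49% without the minimum and 0.7% with it.

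As a rough check, the chance at a single scan for the 10 mm lesion in this model is 1.7-4.6%. Treating the scans as independent, 1 - (1 - 0.017)^8 = 12.8% and 1 - (1 - 0.046)^8 = 31.4%, close to the simulated range. The scans share one baseline reading, so exact agreement is not expected.

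**4. If the next scan must also show PD.** At 10 mm the 13-30% falls to 0.3-2.0%, and the 49% at an SD of 1.5 mm falls to 9%.

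**5. Which endpoint moves.** The simulated lesions are stable, so these patients are non-responders whether scored SD or PD. The rates in step 3 therefore describe false PFS events. They do not measure how often a responder is mislabelled. For a lesion still unchanged at week 6, the chance of a false PD at that scan is the single-scan figure of 1.7-4.6% at 10 mm.

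**The case against.** The strongest reply is that RECIST 1.1 is named throughout as the standard, so Table 12.1 is shorthand, and that the verification rule already deals with a 2 mm change in one small lesion. Step 4 shows that confirmation would remove most of the excess. This stands in part. But Table 12.1 is the only target-lesion PD rule that the documents print, and it is the one that a reader scoring scans will apply. Verification is tied to progression being equivocal, and nothing labels a reading that meets the printed threshold as equivocal. A patient taken off for PD is also outside the Section 9.1 provision for continued scheduled scans, which covers those who stop for other reasons. The Section 10.0 calendar lists a tumour assessment at the final visit, about 100 days after the last dose, but does not say that it can confirm or withdraw an earlier PD.

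The second reply is that Section 14.0 counts as a responder anyone with a complete or partial response at any point during nivolumab treatment, with no cut-off at progression. This stands. A reader might infer that a false PD turns responders into non-responders in every Section 14.0 comparison. The documents do not support that: a later response still counts under Section 14.0 while treatment continues, and only the Section 12.1 window would exclude it.

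Three other stronger readings also fail:

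- **A 1 mm difference is PD.** A reader might combine the 5 mm default with 6/5 = 1.20. That requires the smallest on-study sum as reference, which the plan never states. Against a 10 mm baseline, 6 mm is a 40% decrease, and PD would need 12 mm.
- **Small sums will be common because disease is resected before baseline.** Resection is optional, up to five lesions are targets, and they are chosen by size. No figure is given for the number of patients with small sums.
- **The 5 mm default marks the limit of reliable measurement.** The same paragraph has actual measurements recorded even when smaller than that.

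**Conclusion.** The point holds in a limited form. As printed, the PD rule has no absolute minimum, and a sole 10 mm target read as 12 mm is PD whether the reference is baseline or the smallest sum. Over eight scans against baseline the false-PD chance for a stable lesion is about 13-30% at 10 mm, fading to about nil by 30 mm. This assumes a reading SD of 0.75 to 1.0 mm, a single target, independent errors and no confirming scan. The overall effect on the 30 patients cannot be computed, because the distribution of baseline sums is not given.

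The main consequence is spurious PFS events, in an analysis that Section 14.0 lists as optional. Loss of a true response is possible under the Section 12.1 best-overall-response window but was not quantified, and it depends on which of the two responder definitions is used. The study is descriptive and sized on feasibility, so this does not threaten its design. It is a scoring rule that should be put right because doing so is so cheap.

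**What to change.** For endpoint scoring of best overall response and PFS:

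1. Amend the PD row of Table 12.1 to require at least a 20% increase in the sum of diameters and an absolute increase of at least 5 mm, or the appearance of new lesions. The 5 mm figure is a proposal supported by the error rates above; the documents do not supply it.
2. State in the same row which sum the increase is measured from, and reconcile the row with the RECIST 1.1 criteria that the protocol names as governing.
3. Reconcile the best-overall-response window in Section 12.1 with the responder definition in Section 14.0, so that a response after a first PD scan is handled in one way.

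This costs one clause and two clarifying sentences, with no new data. The downside is that true growth of a very small lesion may be called one scan later. Sums of 25 mm or more are scored exactly as now. The change concerns scoring only. On when treatment ends, Sections 4.3 and 13.0 refer to confirmed progression while Sections 5.1 and 9.1 refer to progression. The sponsor should reconcile those passages separately, and no position is taken on them here.
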